Safety analyses, based on the Safety Population, will involve examination of the descriptive statistics and individual patient listings for any effects of study treatment on clinical tolerability and safety. Summaries will be prepared by treatment group (ie, placebo and LX9211 dose level) and, by study visit where applicable. The incidence of AEs will be presented by severity and by relatedness as assessed by the Investigator. All safety data will be provided in listings.

Treatment-emergent adverse event (TEAE) summaries will include the overall incidence of TEAEs, Incidence of TEAEs (by System Organ Class [SOC] and Preferred Term [PT]), TEAEs by maximum intensity, TEAEs by relationship to study treatment, events leading to discontinuation of study drug, deaths, and SAEs.

Vital signs, ECGs findings, PE findings, clinically significant PE findings, weight, and laboratory parameters (chemistry, hematology, and urinalysis) will be summarized descriptively at each time point. Actual and change from Baseline data will be calculated and summarized. In addition, shift table analyses will be presented for the laboratory data.

Table of Contents

1.	Syn	opsis		3
2.			eviations and Definitions of Terms	
3.	3.1		round on LX9211 and Neuropathic Pain	
	3.2	_	1 Nonclinical Pharmacology, Pharmacodynamics, and Toxicology	
		3.2.1	In Vitro Pharmacodynamic Studies	2 €
		3.2.2	In Vivo Pharmacodynamic Studies	
		3.2.3	Safety Pharmacology	
		3.2.4	Summary of Pharmacology	
		3.2.5	LX9211 Toxicology	
		3.2.6	Preclinical GLP-Compliant Toxicology Studies in Rats	28
		3.2.7	Preclinical GLP-Compliant Toxicology Studies in Dogs	
		3.2.8	Embryo-Fetal Development Study in Rats	30
		3.2.9	Embryo-Fetal Development Study in Rabbits	30
	3.3	Clinica	al Trials of LX9211 in Humans	31
	3.4	Ration	ale for Current Study	32
		3.4.1	Rationale for Selection of Dose	32
	3.5	Ration	ale for Study Design and Control Groups	33
4.	Stuc	ly Objec	tives	33
	4.1	Primar	y Objective	33
	4.2	Second	dary Objective(s)	33
	4.3	Other 0	Objective(s)	33
5.	Inve	stigation	nal Plan	34
	5.1	Overal	1 Study Design	34
Figu	re 5.1	−1 Tre	eatment Schema	35
		5.1.1	Screening Period	36
		5.1.2	Run-in Period	36
		5.1.3	Randomization/Treatment Period	36
		5.1.4	Safety Follow-up Period	
		5.1.5	Optional Substudies.	
6.		-	ation	
	6.1			
	6.2		ion Criteria	
	6.3	Criteri	a for Stopping Treatment/Study Withdrawal	
		6.3.1	Lost to Follow-up	43

	6.4	Criteri	a for Term	ination of the Study	43

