10.4.5.3 Clinical Laboratory Parameters

Laboratory results will be reported in Conventional units and Systeme International (SI). Clinical laboratory value observed at Baseline (predose), at each time point, and changes from Baseline to each assessment time point will be summarized using descriptive statistics and presented by treatment group. Additionally, each patient's laboratory results will also be classified into Low, Normal, and High according to standard normal ranges and summarized using shift tables, comparing the Baseline and each assessment time point. Percentages will be based on the

number of patients with both non-missing baseline and relevant postbaseline results. A by-patient data listing of all clinical laboratory test results will be provided.

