10.4.5.6 Electrocardiogram (ECG)

The actual values of the 12-lead ECG parameters at Baseline, at each time point, and change from Baseline will be summarized using descriptive statistics. The number and percentage of patients with at least 1 post Baseline abnormal ECG result will be summarized using descriptive statistics and presented by treatment group.

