6.1.2 Secondary efficacy and other efficacy endpoints based on data collected at clinic visits

The rest of the efficacy endpoints based on data collected at clinic visits will follow the visit windows defined in [Table 1.2](#).

Table 1.2 Definition of visit windows for efficacy data collected at each visit

Visit	Target Day of Visit ^a	Acceptable visit window
Screening	Day -28	NA
Run-in ^b	Day -14	NA
Baseline	Day 1	Day 1 to Day 4
Week 2	Day 15	Day 5 to Day 22
Week 4	Day 29	Day 23 to Day 36
Week 6	Day 43	Day 37 to Day 60
Week 11	Day 78	Day 61 to 35 days after the last treatment dose during the double-blind Treatment Period

^a relative to the date of first dose of study drug during the double-blind Treatment Period/date of Randomization/date of Baseline Visit (Day 1)

^b weight is collected

In general, the Baseline value for a variable is defined the last value collected or taken on or before Day 1 and prior to the first dose of double-blind study drug. In cases where there are multiple such values, the non-missing value closest to the start of study treatment is selected. If time is available for an assessment on Day 1, it will be compared with dosing time on Day 1 to define the Baseline value.

Multiple visits within the same window will be dealt with as follows:

- If both scheduled and unscheduled visits fall within the same visit window, the scheduled visit will be used for analysis.
- If multiple scheduled visits occur within a single visit window, then the visit closest to the target day of the visit window will be used in the analysis. If there is a tie, the later visit will be used in the analysis.

- If multiple unscheduled visits occur within a single visit window (with no scheduled visit within the window) then the unscheduled visit closest to the target day of the visit window will be used in the analysis. If there is a tie, the later unscheduled visit will be used in the analysis.

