7.7.3 Laboratory Evaluations

Data for the following hematology, serum chemistry, lipid panel, and urinalysis analytes received from central laboratory will be listed and summarized by treatment group and visit. If data for any additional analytes are also received, then these will be listed only.

Hematology	Serum Chemistry	Urinalysis
Complete blood count (CBC) with differential Platelet count	Albumin Alkaline phosphatase Alanine transaminase (ALT) Amylase Aspartate transaminase (AST) Total bilirubin Glucose Blood urea nitrogen (BUN) Calcium Carbon dioxide Chloride Creatinine Magnesium Phosphorus Potassium Sodium Total protein Uric acid	Appearance Color Glucose Ketones Nitrite pH Protein Specific gravity Occult blood Leukocyte esterase Bilirubin Urobilinogen Urine microscopy White Blood Cell Red blood Cell Epithelial cells Bacteria Casts Crystals
Lipid panel	Other Samples	
High-density lipoprotein (HDL) Low-density lipoprotein (LDL) Total cholesterol Triglycerides Creatinine phosphokinase (CPK)	Pregnancy tests (females only) Urine screen (drugs of abuse and THC)	

All laboratory data will be reported in International System of Units and conventional units. Out-of-reference-range values will be flagged as high (H) or low (L) in the listings.

For analysis purposes, values preceded by a "<" or a ">" sign (ie, those below or above the limits of quantification) will be considered equal to the lower or upper limit of quantification, respectively.

Laboratory data will be summarized by visit using standard descriptive statistics by treatment group and overall for the Safety population. Changes from Baseline will also be summarized.

For hematology and serum chemistry, shift tables presenting movement in and out of reference range from Baseline to each scheduled post-Baseline visit will be provided by treatment group and overall for the Safety population. Percentages will be based on the number of patients with both non-missing Baseline and relevant post-Baseline results.

For each laboratory analyte, the Baseline value will be defined as last scheduled or unscheduled value collected prior to the first dose of study drug during the double-blind Treatment Period. Assessments carried out on the day of first study drug administration are considered to have taken place before the study drug administration, if the corresponding times have not been recorded.

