7.7.5 Electrocardiograms

The following quantitative ECG measurements will be taken during the study:

- Heart rate (beats/min)
- PR interval (msec)
- QRS duration (msec)
- QT interval (msec)
- QTc interval (msec)
- Fridericia corrected QT (QTcF) interval (msec)
- RR interval (msec)

The ECG measurements and changes from Baseline in ECG will be listed and summarized by visit using standard descriptive statistics by treatment group and overall for the Safety population.

The Baseline value will be defined as last scheduled or unscheduled value collected prior to the first dose of study drug during the double-blind Treatment Period. Assessments carried out on the day of first study drug administration are considered to have taken place before the study drug administration, if the corresponding times have not been recorded.

An overall Investigator assessment of ECG will be provided (categories "normal", "abnormal, not clinically significant", "abnormal, clinically significant", "indeterminate", "not evaluable", and "unknown").

The Investigator assessment will be listed and the number and percentage of patients within each assessment category will be tabulated by visit, treatment group and overall for the Safety population. Shifts from Baseline (normal vs. abnormal, not clinically significant vs. abnormal, clinically significant) at each post-Baseline visit will be presented by treatment group and overall for the Safety population.

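### The SAP drops the protocol's count of patients with any abnormal post-Baseline ECG and, secondarily, gives no urinalysis shift table; neither change is declared

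*SAP*

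**What the plan says.** **ECG.** Protocol 10.4.5.6 commits to a patient-level result, presented by treatment group: "The number and percentage of patients with at least 1 post Baseline abnormal ECG result will be summarized using descriptive statistics". SAP 7.7.5 tabulates the investigator's overall assessment by visit and adds: "Shifts from Baseline (normal vs. abnormal, not clinically significant vs. abnormal, clinically significant) at each post-Baseline visit will be presented by treatment group". It contains no count taken across visits.

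**Urinalysis.** The protocol synopsis (Safety Data Analysis) says that "laboratory parameters (chemistry, hematology, and urinalysis) will be summarized descriptively at each time point" and continues: "In addition, shift table analyses will be presented for the laboratory data". Protocol 10.4.5.3 has each patient's laboratory results "classified into Low, Normal, and High according to standard normal ranges and summarized using shift tables, comparing the Baseline and each assessment time point", with no panel left out. SAP 7.7.3 is narrower: "For hematology and serum chemistry, shift tables presenting movement in and out of reference range from Baseline to each scheduled post-Baseline visit". It does keep a by-visit summary, since "urinalysis analytes received from central laboratory will be listed and summarized by treatment group and visit".

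**Declared changes.** SAP 8 lists one change, the NPSI model. The version history in SAP Appendix 1 mentions Protocol Amendment 4 and dry-run comments, and names neither omission.

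**Windows.** SAP 6.1.3 applies the Table 1.2 visit windows to laboratory, vital-sign, ECG and physical-examination data. SAP 6.1.2, which holds that table, also has a rule for several visits in one window: "If both scheduled and unscheduled visits fall within the same visit window, the scheduled visit will be used for analysis".

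**The concern.** The protocol's ECG result answers a simple question: how many patients in each arm had an abnormal tracing at any time after Baseline. By-visit tables answer a different one. With no declaration in SAP 8, a reader of the study report cannot tell whether the promised result was dropped on purpose or overlooked.

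Both outputs bear on signals the protocol itself raises. Protocol 3.2.3 reports hERG inhibition and a slightly prolonged QTc in one dog, and exclusion criterion 11 removes patients with risk factors for torsade. Protocol 9.1.1.1 describes urinary bladder findings in dogs and says bladder-related events will be closely monitored. What is at stake is the completeness of descriptive safety tables by arm. No hypothesis test is involved.

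**Working it through.** There is no stated figure to reproduce; the check is a comparison of texts plus one counting argument.

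**1. Can the by-visit tables give the any-time count?** The Schedule of Events places post-Baseline ECGs at Week 6 (or end of treatment/early withdrawal) and Week 11. Let a patients be abnormal at Week 6, b at Week 11 and c at both, among n. Then

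any-time count = a + b − c.

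The by-visit tables give a and b but not c. Since c cannot exceed the smaller of a and b, and can be as low as zero when a + b ≤ n, the count lies between max(a, b) and a + b.

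With n = 94 (the planned arm size) and assumed by-visit counts:

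- a = b = 5: from 5 to 10 patients, 5/94 = 5.3% to 10/94 = 10.6%.
- a = b = 6: from 6 to 12 patients, 6/94 = 6.4% to 12/94 = 12.8%.

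When the two by-visit counts are equal, the any-time count is uncertain by a factor of two. The shift tables do not help, because they too are built one visit at a time. This holds for scheduled ECGs alone.

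**2. Does Table 1.2 matter for a restored count?** It does in two places, so the count should not depend on window assignment.

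- Days 1 to 4 belong to the Baseline row, but the Baseline value must precede the first dose. An unscheduled ECG on Days 2 to 4 therefore has no post-Baseline row.
- The Week 11 row closes 35 days after the last double-blind dose. With a last dose on Day 43 that is 43 + 35 = Day 78. The visit is due on Day 78 with a +7-day allowance, so Days 78 to 85. A permitted visit on Days 79 to 85 falls outside every window, and Week 11 is one of only two scheduled post-Baseline ECGs.

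**3. Urinalysis.** The synopsis names three panels as laboratory parameters and promises shift tables for the laboratory data. SAP 7.7.3 gives shift tables for two of the three. The Low/Normal/High scheme in Protocol 10.4.5.3 needs a numerical reference range. Many items in the SAP's urinalysis list (appearance, color, nitrite, occult blood, leukocyte esterase) do not naturally have one. The commitment therefore carries over directly only to analytes with ranges; for the rest, a normal/abnormal shift is an adaptation of it.

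**The case against.** The other side has several fair points.

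- The ECG gap is narrow: two scheduled post-Baseline tracings, descriptive analysis only. The investigator's assessment is listed for every patient, so the count could be made by hand. The SAP refers to table shells that are not among the documents, and they might contain it. This limits the size of the point. It does not make the SAP text match the protocol, and a listing is not a count by arm.
- Limiting Low/Normal/High shifts to hematology and chemistry is a sensible choice for mostly qualitative urinalysis items, and urinalysis is still summarized by arm and visit. This largely stands. What remains is that the SAP gives no such reason and does not declare the change.
- Adverse-event tables are a real safeguard. Protocol 8.1.1 says clinically significant laboratory values should be reported as adverse events. The definition in Protocol 9.1.1 is broad enough to take in a clinically significant ECG change, although Protocol 8.1.3 says only that such changes may be reported. This stands for clinically significant findings. The protocol's ECG count, however, covers any abnormal result, including those judged not clinically significant.

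A reader might go further and infer from the multiple-visit rule that unscheduled laboratory, vital-sign and ECG values are shut out of the safety tables altogether. The documents do not establish that. SAP 6.1.3 adopts the Table 1.2 rules for assigning observations to visits and does not name the bullets that choose among several visits; those sit in a section on efficacy data. An unscheduled visit is used when its window holds no scheduled one. The SAP also does not say whether the rule works per visit or per assessment, which matters for ECGs, as none is routinely scheduled at Weeks 2 and 4. Nor does the protocol promise a worst-value table for laboratory data or vital signs: Protocol 10.4.5.3 and 10.4.5.4 speak only of assessment time points.

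**Conclusion.** The ECG point holds on the text alone: a promised patient-level count is missing from the SAP, cannot be rebuilt from the tables that replace it, and is not declared in SAP 8. The urinalysis point holds in weaker form, as an undeclared narrowing with a partly good reason behind it.

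Severity is minor, and no efficacy result changes. The ranges of 5 to 10 and 6 to 12 patients rest on assumed by-visit counts and the planned 94 per arm; they illustrate what is unrecoverable and do not estimate an actual loss. The documents give no number of affected patients and no direction of effect.

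The conclusion does not rest on any claim that unscheduled values are excluded from safety summaries. How the multiple-visit rule applies to safety data is an ambiguity worth settling, and the protocol leaves any-time rows for laboratory data and vital signs to the sponsor's choice.

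**What to change.** 1. In SAP 7.7.5, restore the number and percentage of patients per arm with an abnormal ECG at any time after the first dose. Count every post-dose ECG, scheduled or unscheduled, whatever its visit window.
2. In SAP 7.7.3, add a shift table for urinalysis analytes that have reference ranges, and a normal/abnormal shift for occult blood, leukocyte esterase, protein and nitrite, the four results that trigger microscopy under Protocol 8.1.1. Otherwise, declare the omission in SAP 8 with the reason.

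Optional, and not restoring any protocol commitment: a sentence in SAP 6.1.3 saying whether the multiple-visit rule applies to safety data, and whether per visit or per assessment; and any-time (worst-value) rows in the hematology, chemistry and vital-sign shift tables.

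The cost is one extra count, one extra table and a few lines of SAP text. All the data are already collected, and the scheduled-visit rule can stay for by-visit summaries.

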5.1.5 Optional Substudies

During the Screening Visit, patients may choose to participate in 1 or both of the 2 optional substudies.

The first substudy will include approximately 30 patients for intensive blood sampling for determination of LX9211 plasma concentrations to allow for PK parameter estimation, and additional samples for possible biomarker analyses. The PK intensive sampling will occur on Days 1 and 2 and at the Week 6 clinic visit. These patients will be confined to a clinical research unit (CRU) twice during the study for intensive PK evaluation and biomarker evaluation: prior to

and following the first dose of study drug and prior to and following their final dose of study drug (planned for Week 6).

The second optional substudy, a qualitative patient interview, will include approximately 60 patients. The telephone interview will be designed to gain insight and understanding of patients' experiences with symptoms of DPNP and to assess relevance and clinical meaningfulness of symptom improvements (eg, reduction in pain) with LX9211 treatment.

6. Study Population

Up to 282 patients (94/treatment group) are expected to enroll in this study in order to complete 225 (75/treatment group). The sample size may be increased to a maximum of 351 patients based on a planned interim analysis that allows for conduct of a sample size reestimation procedure.

A subset of approximately 30 patients will be recruited to participate in the PK and biomarker analyses optional substudy.

A second substudy will enroll a minimum of 60 patients and not to exceed 85 patients to participate in a qualitative patient interview.

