10.1 Determination of Sample Size

Proposed Sample Size

A sample size of 75 patients per treatment group who complete the 6-week double-blind Treatment Period will yield 80% power to detect a true mean difference of 1 unit between at least 1 of LX9211 treatment groups and placebo in ADPS change from Baseline, assuming a common standard deviation of 2 and an overall significance level of α=0.05 (2-sided Dunnett's test). Accounting for a dropout rate of 20%, a total of 282 patients (94 patients per treatment group) will be enrolled and randomly assigned to treatment in a 1:1:1 ratio. This sample size is adjusted for the multiple comparisons of each LX9211 treatment group with placebo (Westfall, 1999).

Sample Size Reestimation

Due to the uncertainty in the outcome for the primary endpoint analysis secondary to potential variations in some of the key design parameters such as the dropout rate and standard deviation associated with the targeted treatment group difference, an unblinded SSR adaptation will be implemented at the time of the interim analysis testing for futility. This will occur when the first 141 patients have been accrued and followed thru Week 6 or dropped out early from the trial (whichever event happens first). Should a patient drop out early in the study, but return for the Week 6 visit, the Week 6 data will be used in the analysis. The Chen-DeMets-Lan method will be used for the unblinded SSR since it requires minimal change from a group sequential test. This method requires specification for a number of criteria related to the allowable conditions for increasing the sample size that ensures that ordinary group sequential methods can be applied while seeing that the overall error is not inflated compared to the original group sequential design. The 2 primary conditions which are required and satisfied in the SSR for this study are that (a) the SSR is made at the penultimate look, and (b) the conditional power at the penultimate look occurs between 50% and 80.3% (the original specified power under the group sequential design). The SSR is linked to the projected effect size falling within this "promising" or "favorable" range of conditional power. Having satisfied these 2 main conditions, the Type I error rate after increasing the sample size until the conditional power equals the original target power will not be greater than the Type I error from the originally proposed design.

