10.4.5.7 Interim Analysis

An interim analysis of the primary endpoint will be performed to test for futility when 50% of the planned information has been accrued. This will occur when the first 141 patients have been accrued and followed to endpoint at Week 6 or dropped out from the trial earlier, whichever event occurs first. Should a patient drop out early in the study, but return for the Week 6 visit, that Week 6 data will be used in the analysis.

A non-blinding futility boundary will be used to test treatment group differences in the primary endpoint at 50% of the original planned information. The set of boundary values will be derived by using a beta spending function and specification of a power family with value = 3.672. The monitoring boundary is constructed by assuming a 1-sided test with a per comparison Type I error rate = 0.0141, assuring an overall α = 0.025 (or a two-sided α = 0.05) for the two LX9211 versus placebo comparisons. Use of this beta spending function for futility testing is conservative and results in cumulative beta error rates of 0.015 and 0.197 at the interim and final analyses, respectively. Application of the futility analysis is to serve as a guideline and is not the only source of information used to evaluate the trial for a negative finding. Assessment of other data available at the interim analysis will be used to qualify the trial for a recommendation of futility (eg, secondary and other efficacy variables , safety data).

The futility analysis will be described in the SAP and DMC Charter documents.

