6.1.3 Safety analyses

Safety analyses for the laboratory assessments, vital signs, ECG and physical exam data will use the study visit window rules used to assign observations to visits as defined above in [Table 1.2](#).

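### Assigning safety visits by study day alone keeps early-withdrawal values before Day 37 out of the Week 6 row and lets off-drug follow-up values into it

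*SAP*

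**What the plan says.** SAP 6.1.2, Table 1.2, sets the windows: Baseline Days 1-4, Week 2 Days 5-22 (target Day 15), Week 4 Days 23-36 (target Day 29), Week 6 Days 37-60 (target Day 43), and Week 11 from Day 61 to 35 days after the last double-blind dose. If several scheduled visits share a window, "then the visit closest to the target day of the visit window will be used in the analysis", with ties going to the later visit. A scheduled visit takes precedence over an unscheduled one. EW visits have no exception.

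SAP 6.1.3 carries this over to safety: "Safety analyses for the laboratory assessments, vital signs, ECG and physical exam data will use the study visit window rules". The tables are by visit; for example, SAP 7.7.5 states "The ECG measurements and changes from Baseline in ECG will be listed and summarized by visit". Neither the laboratory, vital-sign nor ECG section has an end-of-treatment, last-on-treatment or worst-value row.

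The schedule of events (Protocol Appendix A, SAP Appendix 2) places the EW visit in the Visit 6 column. After Day 1, ECG is scheduled only at Visits 6 and 7, and hematology only at Visit 6. Chemistry, urinalysis and vital signs are taken at every visit from Day 1 to Visit 7. Footnote b places the follow-up visit 35 days after the last dose, with a +7-day window.

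**The concern.** For ECG and hematology, Visit 6 or its EW equivalent is the only scheduled on-treatment assessment after Day 1. A reader will take the Week 6 row as the end-of-treatment picture. Under the windowing rule, on-drug values from patients who stopped before Day 37 do not appear there, although that is the column in which the schedule collects them. Some of these patients reappear in the row with a value taken five weeks after stopping.

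The affected patients include any who stop for tolerability. Safety is a stated objective, and Protocol 3.2.3 reports hERG inhibition and a slight QTc prolongation in one dog, so the ECG row will be read closely.

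**Working it through.** **Size of the group.** Protocol 10.1: "Accounting for a dropout rate of 20%, a total of 282 patients (94 patients per treatment group". Check: 75/(1 - 0.20) = 93.75, rounded up to 94; 3 x 94 = 282, as stated. Protocol Section 6 plans 282 "in order to complete 225 (75/treatment group" completing, so 282 - 225 = 57 planned non-completers. If re-estimation raised the total to 351, 20% would be about 70.

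**Assumption.** The documents do not give the day of withdrawal. I take the EW visit to fall on the last-dose day, uniformly over Days 2-42 (41 possible days), and then vary the timing.

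**Rule applied day by day**, with routine visits on Days 15 and 29 and the tie-break run per visit:

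| EW day | Result | Share | Of 57 |
|---|---|---|---|
| 2-4 | Baseline window, no post-Baseline row | 3/41 = 7.3% | 4.2 |
| 5-15 | Week 2 | 11/41 = 26.8% | 15.3 |
| 16-22 | Dropped (Week 2 visit nearer Day 15) | 7/41 = 17.1% | 9.7 |
| 23-29 | Week 4 | 7/41 = 17.1% | 9.7 |
| 30-36 | Dropped (Week 4 visit nearer Day 29) | 7/41 = 17.1% | 9.7 |
| 37-42 | Week 6 | 6/41 = 14.6% | 8.3 |

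The share missing Week 6 is 35/41 = 85%. The share dropped by the tie-break is 14/41 = 34%, or 26% if routine visits vary uniformly by +/-3 days.

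**Per-observation reading.** SAP 6.1.3 speaks of assigning observations. Read that way, ECG and hematology have no routine competitor at Weeks 2 or 4, so the tie-break drops none of them: 18/41 (44%) go to Week 2, 14/41 (34%) to Week 4, 3/41 (7%) to the Baseline window and 6/41 (15%) to Week 6. The 85% is unchanged.

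**Range of timings.** All withdrawals on Days 2-14, or on Days 2-28: 100% miss Week 6. All on Days 29-42: 8/14 = 57% miss it.

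**Follow-up visit.** Last dose on Day d puts follow-up on Day d + 35, which lies in Days 37-60 when d is 2-25. That is 24/41 = 59% of early stoppers, about 33 of 57 if all attend. If every follow-up used the full +7 days, d would be 2-18: 17/41 = 41%. For d below 26 the Week 11 window is empty, because d + 35 is below 61. Protocol 3.3 gives a mean half-life of 143-197 hours; 35 days is 840 hours, or 840/197 = 4.3 to 840/143 = 5.9 half-lives, so these values are largely washed out.

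**One patient.** Week 2 visit on Day 15, EW visit and last dose on Day 20, follow-up on Day 55. Read per visit, the Day 20 ECG is dropped; read per observation, it is filed under Week 2. On either reading the Day 55 ECG is filed under Week 6.

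**The case against.** Filing by actual study day is a legitimate convention. A value placed under Week 2 or Week 4 stays tabulated at its true exposure time, and SAP 7.7.5 shows ECG shifts at each post-Baseline visit. This stands: such values are displaced, not lost. Hematology is less well covered, since SAP 7.7.3 limits its shift tables to scheduled post-Baseline visits.

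Other outputs carry much of the signal. Laboratory abnormalities that are clinically significant, need treatment or lead to discontinuation are reported as adverse events (Protocol 9.1.1), adverse event tables do not use the windows, and all data are listed. This also stands. One backstop is missing, however: Protocol 10.4.5.6 promises a count of patients with any post-Baseline abnormal ECG, but SAP 7.7.5 does not carry it over and SAP Section 8 does not list the omission.

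The counts rest on assumed timing and full attendance, whereas Protocol 6.3 only encourages completion of the end-of-study assessments. Nor do the documents say that the EW visit falls on the stopping day. Both limits apply to the figures above.

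A reader might infer three stronger claims that the documents do not support:
- That the Week 6 row contains only patients treated to about Day 37. The follow-up arithmetic shows otherwise.
- That ECG and hematology of early stoppers are generally discarded. That needs the per-visit reading of the tie-break.
- That the tables will favour LX9211. Neither the pattern of stopping nor the direction of any bias can be known from the plan.

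**Conclusion.** The point holds as a defect in the windowing rule; it should be corrected but does not threaten the trial. Two results follow from the text without any timing assumption: no EW visit on Days 2-36 reaches the Week 6 row, and an attended 35-day follow-up after a last dose on Days 2-25 is filed as Week 6. Hematology escapes the second effect because it is not drawn at follow-up.

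The percentages are conditional on uniform withdrawal, except the 57-100% range for missing Week 6, which covers the timings tested. At the planned size, 57 is an upper figure for the number of patients, because attendance is not assured. Whether ECG and hematology values are dropped or only refiled depends on a reading that the SAP leaves open.

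**What to change.** In SAP 6.1.2 and 6.1.3, with the matching table sections:

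- Add a row for the end of double-blind treatment, equal to the Visit 6 or EOT/EW value whatever its study day, for ECG, laboratory parameters, vital signs and the shift tables.
- Apply the closest-to-target rule per parameter among non-missing values, so that a visit without an ECG cannot displace one that has it.
- Assign the 35-day follow-up visit to the follow-up row regardless of study day, so that it cannot enter Week 6. The added row alone would not achieve this.
- Restore the Protocol 10.4.5.6 summary of patients with at least one post-Baseline abnormal ECG.

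The cost is SAP wording, one extra row per safety table and one ECG summary; no new data are needed. The downside is that the added row mixes different durations of treatment. Keeping the by-day rows beside it, and stating the mixture in a footnote, deals with that.
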